15.4. Appendix 4: Study Phases and Treatment State

15.4.1. Study Phases

Assessments and events will be classified according to the time of occurrence relative to the Treatment Start Date defined in Section 15.6.1.

AEs will be assigned to study phases as defined in Table 13. For example, adverse events on/after start of maintenance phase IP and prior to start of Extension phase IP/LTFU ART will be assigned to the Maintenance Phase.

Laboratory data (efficacy, safety, PK and virology), HIV associated Conditions, health outcomes assessments, vital signs, and ECGs will be assigned to study phases as defined as in Table 14. For example, assessments/events occurring after start of maintenance phase IP and up to and including start of extension phase IP/LTFU ART will be assigned to the Maintenance Phase.

Assessments/events are assigned to study phases sequentially, starting from the top of each table. No study phases will be assigned to medications.

Table 13 Assignment of Study Phases for AEs

Study Phase	Definition
Screening	Date < Maintenance Treatment Start Date
Maintenance	
For participants continuing into Extension Phase: Maintenance Treatment Start Date ≤ Date < Date of Nominal Week 100 Visit
 
For participants not continuing into Extension Phase^[a]: Maintenance Treatment Start Date ≤ Date < LTFU ART Start Date For AEs leading to withdrawal and started on the same date as LTFU ART Start Date, Maintenance Phase, instead of Long-term Follow-up phase, will be assigned.

Extension	
Participants continuing into Extension Phase^[a]: Date of Nominal Week 100 Visit ≤ Date < LTFU ART Start Date For AEs leading to withdrawal and started on the same date as LTFU ART Start Date, Extension Phase, instead of Long-term Follow-up phase, will be assigned.

NOTES:

- Date = AE Start date
- [a] If participants have missing LTFU ART start date, only the lower bound will be considered in the derivation.

Table 14 Assignment of Study Phases for Lab Assessments (including PK and Virology), ECG, Protocol Deviations, Vital Sign, Health Outcomes, HIV Associated Conditions

Study Phase	Definition
Screening	Date \leq Maintenance Treatment Start Date Note: 2-hour post-dose ECG taken on the Maintenance Treatment Start Date will be excluded.
Maintenance	For participants continuing into Extension Phase: Maintenance Treatment Start Date < Date \leq Date of Nominal Week 100 Visit Note: 2-hour post-dose ECG taken on the Maintenance Treatment Start Date will be included. For participants not continuing into Extension Phase^[a]: Maintenance Treatment Start Date < Date \leq LTFU ART Start Date Note: 2-hour post-dose ECG taken on the Maintenance Treatment Start Date will be included.
Extension	Participants continuing into Extension Phase^[a]: Date of Nominal Week 100 Visit < Date \leq LTFU ART Start Date

- Date = start or assessment date
- [a] If participants have missing LTFU ART start date (i.e. the participants have not started ART in LTFU yet), only the lower bound of the window will be considered in the derivation.

Table 15 Assignment to Long-term Follow-up Phase

Study Phase	Definition
Long-term Follow-up	Date > max (Last IM Injection Date, Last Oral Bridging End Date)

- Date = Assessment/Start Date
- For AEs leading to withdrawal and started on the same date as LTFU ART Start Date, maintenance phase or extension phase depending on participant's continuation status to extension phase, instead of long-term follow-up phase, will be assigned. Refer to [Table 13](#) for details.

Only participants who received at least one CAB and/or RPV injection will enter the long-term follow-up. Note that the long-term follow-up phase and maintenance/extension phases are not necessarily mutually exclusive and are to be defined with separate phase variables in the datasets. For example, an Q4W IM participant who has Week 44 injection and withdrawal at Week 48 without receiving Week 48 injection, the “Week 48 withdrawal visit” belongs to both the maintenance phase and long-term follow-up phase.

15.4.2. Treatment State

Within each treatment study phase (i.e. Maintenance and Extension—based on assignment of study phase described in Section [15.4.1](#)), only those assessments which occur within the ranges shown in [Table 16](#) will be considered ‘on-treatment’ for the given phase. No treatment states will be assigned to medications.

Table 16 Treatment State within Study Phases^b

Study Phase ^a	Treatment State	Date Range
Screening	Pre-treatment	All assessments/events within the phase
Maintenance	On-treatment	Q8W arm: Date ≤ max (Date of Last Injection + 63, Date of Last Dose of Oral CAB+RPV + 1)
		Q4W arm: Date ≤ max (Date of Last Injection + 35, Date of Last Dose of Oral CAB+RPV + 1)
	Post-treatment	Q8W arm: Date > max (Date of Last Injection + 63, Date of Last Dose of Oral CAB+RPV + 1)
		Q4W arm: Date > max (Date of Last Injection + 35, Date of Last Dose of Oral CAB+RPV + 1)
Extension	On-treatment	Q8W arm: Date ≤ max (Date of Last Injection + 63, Date of Last Dose of Oral CAB+RPV + 1)
		Q4W arm: Date ≤ max (Date of Last Injection + 35, Date of Last Dose of Oral CAB+RPV + 1)
	Post-treatment	Q8W arm: Date > max (Date of Last Injection + 63, Date of Last Dose of Oral CAB+RPV + 1)
		Q4W arm: Date > max (Date of Last Injection + 35, Date of Last Dose of Oral CAB+RPV + 1)
Long-term Follow-up	On-treatment	Q8W arm: Date ≤ min (LTFU ART start date, max (Date of Last Injection + 63, Date of Last Dose of Oral CAB+RPV + 1))
		Q4W arm: Date ≤ min (LTFU ART start date, max (Date of Last Injection + 35, Date of Last Dose of Oral CAB+RPV + 1))
	Post-treatment	Q8W arm: Date > min (LTFU ART start date, max (Date of Last Injection + 63, Date of Last Dose of Oral CAB+RPV + 1))
		Q4W: Date > min (LTFU ART start date, max (Date of Last Injection + 35, Date of Last Dose of Oral CAB+RPV + 1))
NOTE:		

 • Date = Assessment/Start Date. a. Treatment State is determined after data has been assigned to the study phases as defined in Section 15.4.1. b. Last injection and/or last dose of oral CAB+RPV are only applied to participants who permanently discontinued the study treatment. The assessments for participants who did not permanently discontinue the study treatment will be considered 'On-treatment'. For participants continuing into extension phase, all data assigned to maintenance phase per Section 15.4.1 will be considered 'On-treatment'. 		

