	
analysis timepoint of interest for Week 48 analysis (i.e. the date of last on-treatment viral load up to Study Day 378): two or more injection intervals affected by over dosage deviations.
 
 • For participants who received injections beyond the analysis timepoint of interest for Week 48 analysis (i.e. the date of last on-treatment viral load up to Study Day 378): three or more injection intervals affected by over dosage deviations. 
3. $\geq 10\%$ of total time on-treatment with under dosing deviations. The percentage of total time on-treatment with under dosing deviations will be calculated by (the total number of non-compliant dosing days / the total number of intended exposure days) * 100%.
 
Number of Intended Exposure Days = Date of Last Viral Load – Start Date of Study Treatment + 1, where the last viral load refers to the last on-treatment viral load up to Study Day 378 during maintenance phase for Week 48 analysis, and the last on-treatment viral load up to Study Day 714 during maintenance phase for Week 96 analysis.
 
The total number of non-compliant dosing days up to the analysis timepoint visit (or date of IP discontinuation/ withdrawal, whichever is earlier), is derived as follows (summing across all instances):
 
 • For Q4W arm participants requiring oral lead-in: 
 ○ Length of time (in days) until next injection from date of dosage deviation (e.g. 2 mL administered instead of 3mL for Week 4B injection, 1ml administered instead of 2 mL for post Week 4B injections). ○ Length of time (in days) in excess beyond 35 days between injections post Week 12 and in excess beyond 28 days for Week 8 and Week 12 (e.g. missed or late injection visit). ○ Length of time (in days) in excess beyond 35 days from last injection until start of oral bridging post Week 12 and in excess beyond 28 days for Week 8 and Week 12. • For Q4W arm participants not requiring oral lead-in: 
 ○ Length of time (in days) until next injection from date of dosage deviation (e.g. 1 mL administered instead of 2 mL). ○ Length of time (in days) in excess beyond 35 days between injections. ○ Length of time (in days) in excess beyond 35 days from last injection until start of oral bridging post Week 12. • For Q8W arm participants requiring oral lead-in: 
 ○ Length of time (in days) until next injection from date of dosage deviation (e.g. 2 mL administered instead of 3mL). ○ Length of time (in days) in excess beyond 63 days between injections post Week 16 and in excess beyond 56 days for Week 8 and Week 16 (e.g. missed or late injection visit). ○ Length of time (in days) in excess beyond 63 days from last injection until start of oral bridging post Week 16 and in excess beyond 56 days for Week 8 and Week 16. • For Q8W arm participants not requiring oral lead-in: 
 ○ Length of time (in days) until next injection from date of dosage deviation (e.g. 2 mL administered instead of 3 mL). ○ Length of time (in days) in excess beyond 63 days between injections. ○ Length of time (in days) in excess beyond 63 days from last injection until

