15.3.5. Assessment Window for PK Concentration Data

For PK concentration data at the withdrawal/unscheduled/LTFU Month 1 visits during maintenance phase (after assignment to study phase per Table 14), the visit will be slotting to the analysis visit per the following steps:

- Identify the ‘last nominal visit’ with the PK pre-dose assessment performed prior to the visit to be slotted during the same study phase
- Identify the nominal visit corresponding to the next planned pre-dose PK assessment visit (excluding visits with storage PK collection), that is subsequent to the ‘last nominal visit’ with PK pre-dose assessment during the same study phase.
- If the nominal visit corresponding to next planned pre-dose PK assessment visit is prior to/at Week 48 visit, the PK assessment at the unscheduled/withdrawal/LTFU Month1 visit will be slotted to this nominal visit corresponding to next planned pre-dose PK assessment visit.
- Otherwise, the PK assessment at the unscheduled/withdrawal/LTFU Month1 visit will be slotted to the earliest nominal visit from the following:
 - Nominal visit corresponding to the next planned pre-dose PK assessment visit
 - The nominal visit of the next planned injection occurring on or after the date of the PK assessment during the same study phase

During maintenance phase, the planned nominal visits for PK Pre-dose are Week 4B, 8, 16, 24, 32, 40, 48, 96 for Q4W arm; and are Day 1, Week 4B, 8, 16, 24, 32, 40, 48, 96 for

Q8W arm while Day 1 is required only for those transitioning from ATLAS on Q4W injections and Week 4B is required only for participants transitioning from oral SOC and requiring oral CAB+RPV lead-in. In addition, the participants on Q8W arm have planned nominal visits at Week 9 and 41 for 1-week post-dose.

For participants requiring oral CAB+RPV lead-in, the planned injection visits are Week 4B, Week 8, continuing every 4 weeks for Q4W arm and continuing every 8 weeks for Q8W arm. For participants not requiring oral CAB+RPV lead-in, the planned injection visits are every 4 weeks starting from Day 1 for Q4W arm and every 8 weeks starting from Day 1 for Q8W arm.

Example 1: If a participant on Q8W arm has the ‘last nominal visit’ (with PK pre-dose assessment) at Week 24 and then withdraws around Week 28, with the last injection at Week 24 and a Maintenance Phase PK assessment labelled at ‘LTFU Month 1’, This PK assessment labelled as ‘LTFU Month 1’ will be slotted to the subsequent planned nominal visit of Week 32.

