 - CDC Stage III at Baseline to new CDC Stage III event;
 - CDC Stage I, II, III at Baseline to Death.

Please refer to Protocol (Appendix 4: CDC Classification for HIV-1 Infection) for defining Stage.

- For the purpose of analysis, the CDC at Baseline and at post-baseline during Maintenance Phase will be derived as below:
 - At Baseline, the 'Baseline CDC stage' for each participant was assessed by investigator and recorded in the eCRF. However, for the analysis, Baseline CDC stage will be rederived based Baseline CD4+ values as well as whether any HIV-associated/AIDS-defining conditions present at baseline per the Criteria's thresholds (Appendix 4 in Protocol).
 - To analyse disease progression, the most advanced post-baseline CDC stage within the period of interest (e.g. Maintenance Phase) will be derived based on the occurrences of new AIDS-defining conditions (please refer to Appendix 4 in Protocol for the list of AIDS-defining Conditions) as well as the nadir value of post-baseline CD4+.
 - For example, if a participant with CDC 'Stage I' at Baseline had the lowest Maintenance Phase CD4+ =120 cell/mm³ without new AIDS-defining conditions, then HIV disease progression for this participant during the Maintenance Phase would be considered as 'CDC stage I at Baseline to CDC stage III'.
 - If a participant with CDC 'Stage II' at Baseline had the lowest Maintenance Phase CD4+ =220 cell/mm³ AND had at least one new AIDS-defining condition, then HIV disease progression for this participant during the Maintenance Phase would be considered as 'CDC stage II at Baseline to CDC stage III'.

Delay in IP Injection

- For participants on the Q4W arm, IM dosing is expected to occur every 4 weeks from Week 4B onwards for those transitioning from SOC (i.e. those requiring oral lead-in) and from Day 1 onwards for those transitioning from CAB+RPV Q4W in ATLAS (i.e. those not requiring oral lead-in). The Delay in IP injection (days) will be calculated as:
 Delay in IP Injection (days) = Injection date - date of preceding injection - 28 days
- For participants on the Q8W arm, IM dosing is expected to occur at Week 4B and then every 8 weeks from Week 8 onwards for those transitioning from SOC (i.e. those requiring oral lead-in) and every 8 weeks from Day 1 for those transitioning from CAB+RPV Q4W (i.e. those not requiring oral lead-in) in ATLAS.

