 - For participants transitioning from SOC on the Q8W arm, if the preceding injection occurs at Week 4B, the Delay in IP injection (days) will be calculated as:
 Delay in IP Injection (days) = Date of Week 8 injection - date of Week 4B injection - 28 days
 - For participants transitioning from SOC on the Q8W arm, if the preceding injection occurs at a visit later than Week 4B, the Delay in IP injection (days) will be calculated as:
 Delay in IP Injection (days) = Injection date - date of preceding injection - 56 days
 - For participants transitioning from CAB+RPV Q4W in ATLAS on the Q8W arm, the Delay in

IP injection (days) will be calculated as:
 Delay in IP Injection (days) = Injection date - date of preceding injection - 56 days

- Delay in IP injection will be grouped into: ≤1, 2-3, 4-7, >7 days.
- The proportion of participants with HIV-1 RNA ≥50 c/mL at Week 48 (Snapshot) will be summarized by last delay in IP Injection. The last delay in IP injection will be the delay in IP injection at Week 48, or the delay in last IP injection prior to Week 48 if a participant did not receive Week 48 injection (i.e. missing visit or withdrawal).

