
 Last on-treatment VL during Week 48 prior to/on the date of change ≥ 50 c/mL 	HIV-1 RNA ≥ 50	Data in window not below 50

 Last on-treatment VL during Week 48 prior to/on the date of change < 50 c/mL 	HIV-1 RNA < 50	

 No VL during Week 48 prior to/on the date of change 	HIV-1 RNA ≥ 50	Change in background therapy
4. If permitted change ^[a] in background therapy during Week 48 AND the last on-treatment VL prior to/on the date of change is ≥ 50 c/mL (NA to this study)		
4.1 this last on-treatment VL occurs prior to Week 48	HIV-1 RNA ≥ 50	Change in background therapy
4.2 this last on-treatment VL occurs during Week 48 but prior to/on the date of change	HIV-1 RNA ≥ 50	Data in window not below 50
5. If none of the above conditions met		
5.1 On-treatment VL available during Week 48		

 Last on-treatment VL during Week 48 ≥ 50 c/mL 	HIV-1 RNA ≥ 50	Data in window not below 50

 Last on-treatment VL during Week 48 < 50 c/mL 	HIV-1 RNA < 50	
5.2 No on-treatment VL during Week 48		
5.2.1 If participants still on study, i.e. a participant has not permanently discontinued the study treatment yet, or if a participant permanently discontinued the study treatment and the upper bound of analysis snapshot window is prior to the following date: Q8W arm: Min[max(Date of last injection + 63, Date of Last Dose of Oral CAB+RPV + 1), Withdrawal Date] Q4W arm: Min[max(Date of last injection + 35, Date of Last Dose of	No virologic data at Week 48 Window	On study but missing data in window

Oral CAB+RPV + 1), Withdrawal Date] , where 'Withdrawal Date' refers to the date the participant failed to complete per corresponding conclusion form.
		

5.2.2 If participants withdraw before/during Week 48 due to
		

5.2.2.1 Safety reasons (e.g. AE/death, liver chemistry stopping criteria, renal toxicity withdrawal criteria, QTc withdrawal criteria etc, as recorded in eCRF Conclusion form)
	
No virologic data at Week 48 Window
	
Disc due to AE/death

5.2.2.2 Non-safety related reasons (e.g. Lack of efficacy, protocol deviation, withdrew consent, loss to follow-up, study closed/terminated, investigator discretion etc, as recorded in eCRF Conclusion Form)
		

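### Table 16 keeps Q8W lead-in participants on-treatment for 63 days after Week 4B, although the next injection is due 28 days later in both arms; a small number of early stoppers may be scored differently by arm

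*SAP*

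**What the plan says.** SAP section 15.4.2, Table 16, fixes the end of on-treatment time separately for each arm:

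- Q8W: "Q8W arm: Date ≤ max (Date of Last Injection + 63, Date of Last Dose of Oral CAB+RPV + 1".
- Q4W: "Q4W arm: Date ≤ max (Date of Last Injection + 35, Date of Last Dose of Oral CAB+RPV + 1".

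A footnote limits the rule to early stoppers: "Last injection and/or last dose of oral CAB+RPV are only applied to participants who permanently discontinued the study treatment". No footnote makes an exception for the Week 4B injection.

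The schedule for lead-in participants is in section 15.3.5: "the planned injection visits are Week 4B, Week 8, continuing every 4 weeks for Q4W arm and continuing every 8 weeks for Q8W arm". The arms therefore diverge only after Week 8. Three other derivations treat the Q8W interval from Week 4B to Week 8 as four weeks:

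- Section 15.6.3, delay in injection: "Delay in IP Injection (days) = Date of Week 8 injection - date of Week 4B injection - 28 days". The Q4W formula subtracts the same number: "Delay in IP Injection (days) = Injection date - date of preceding injection - 28 days".
- Section 15.6.5, evaluable PK window: the Week 8 pre-dose sample of Q8W lead-in participants is grouped with Q4W, at 24 to 32 days.
- Section 15.1.1, over-dosing rule: the threshold is 3 weeks for this interval and 7 weeks for later Q8W intervals.

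The 63-day figure is reused in the Follow-up slot of Table 8, in Appendix 9 step 5.2.1 ("Q8W arm: Min[max(Date of last injection + 63, Date of Last Dose of Oral CAB+RPV + 1), Withdrawal Date"), in Appendix 10 and in the exposure derivation of section 15.6.4.

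**The concern.** Both windows equal the arm's usual injection interval plus 7 days (56 + 7 and 28 + 7). The SAP does not state that reasoning, but the figures fit it. For the one Q8W interval that is 28 days long, the 63-day window runs 35 days past the due date, while the Q4W window runs 7 days past it.

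A lead-in participant who stops after Week 4B has followed the same injection schedule in either arm, so on-treatment status should not depend on the arm. It matters because Snapshot uses only on-treatment viral loads. For a non-safety withdrawal with no data in the Week 48 window, the last on-treatment value decides between HIV-1 RNA ≥50 c/mL and no virologic data. In an open-label non-inferiority comparison, a classification rule that differs by arm for the same history is best removed.

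**Working it through.** The SAP gives no figure of its own to reproduce here. The check is date arithmetic followed by applying the rules to identical histories.

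**Inputs.** The lead-in lasts 28 ± 3 days (section 2.3), so Week 4B is nominally Day 29. The next injection is due 28 days later (15.3.5, 15.6.3). The windows are 63 and 35 days (Table 16). The last oral dose + 1 day does not bind, because the lead-in ends at Week 4B. Maintenance ends at the LTFU ART start date (Table 14). There are about 510 participants per arm, and the margin is 4%.

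**Dates.**

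| Week 4B on | Next due | Q8W window ends (+63) | Q4W window ends (+35) | On-treatment in Q8W only |
|---|---|---|---|---|
| Day 26 | 54 | 89 | 61 | Days 62-89 |
| Day 29 | 57 | 92 | 64 | Days 65-92 |
| Day 32 | 60 | 95 | 67 | Days 68-95 |

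The gap is 63 − 35 = 28 days in each row. With + 35 after Week 4B, the Q8W window would end on Day 64 in the nominal case, as in Q4W.

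**Identical histories through Appendix 9.** Assume Week 4B on Day 29, a non-safety withdrawal, and that ART started after stopping is not itself scored as a change of background therapy.

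- (a) Viral load <50 on Day 57 and 400 on Day 85, ART from Day 90. Q8W: last on-treatment value is 400, so ≥50. Q4W: Day 85 is post-treatment, so no virologic data.
- (b) Viral load 120 on Day 57 and <50 on Day 85, ART from Day 90. Q8W: no virologic data. Q4W: ≥50.
- (c) As (a), but ART from Day 60. No virologic data in both arms.

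The rule can thus add a Q8W failure (a), remove one (b) or do nothing (c).

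**Size.** One reclassified participant moves the Q8W proportion by 1/510 = 0.20 points, two by 0.39 and five by 0.98. As an illustration, take equal failure rates of 1% to 4% (an assumption) and a simple unstratified Wald interval. The upper bound is 1.21 to 2.38 points with no reclassification, 1.46 to 2.61 with one added Q8W failure, and 2.46 to 3.50 with five. All stay below 4.

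**Other derivations.**

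- Appendix 9 step 5.2.1 at Week 48: the window ends on Day 378, which is not before Day 92 or Day 64, so the step changes nothing. At Week 8, if the default upper bound of Day 84 is used, the participant has no viral load in the window and withdraws after Day 84, the step applies in Q8W (84 < 92) but not in Q4W (84 > 64).
- Exposure takes the earlier of the latest Maintenance visit and the window end. Appendix 10 takes the earlier of the discontinuation day and the window end. Each differs by arm only if that visit or day falls after about Day 64.

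**The case against.** The strongest reply is that very little data can fall in the gap. For a Day 29 injection, Days 65-92 are LTFU Study Days 36-63. Table 11 places its targets at LTFU Days 30 and 90, so no planned visit aims at this stretch. A withdrawal visit at the missed Week 8 date (Day 57) is on-treatment in both arms. Stoppers are meant to start HAART, and Table 14 then closes Maintenance in both arms. This stands, and it is why the point is minor. It does not remove the gap: the Month 1/WD slot runs to LTFU Day 63, so a late withdrawal visit or an unscheduled sample would fall inside it.

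A second reply is that treatment up to Week 4B is not proved identical. The volume example naming that visit ("2 mL administered instead of 3mL for Week 4B injection") is for Q4W; the Q8W lead-in example implies 3 mL but names no visit. This also stands, but the finding rests on the shared 28-day schedule, not on volume.

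A third reply is that section 15.1.1 allows Q8W lead-in participants 56 days for the Week 8 injection before counting under-dosing, so a long Q8W allowance may be deliberate. The same section allows 28 days in Q4W and uses a 3-week over-dosing threshold for the same Q8W interval. That is better read as a second inconsistency than as support for Table 16.

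**Conclusion.** The inconsistency is real and minor. Table 16 gives lead-in participants whose last injection is Week 4B 28 more on-treatment days in Q8W than in Q4W, against the SAP's own 28-day interval in both arms. A Week 48 reclassification needs all of the following: permanent stopping after Week 4B and before Week 8, a non-safety withdrawal, no new ART by about Day 64, and a viral load on about Days 65-92 that changes the last on-treatment category. The SAP does not say how many participants would meet these conditions. Few are likely to, and a changed primary conclusion is unlikely.

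A reader might infer a bias against Q8W. The documents do not support that: histories (a) and (b) go in opposite directions. A reader might also infer that every such stopper gains 28 days in every derivation, or that step 5.2.1 alters the primary endpoint. Neither follows: 28 days is a ceiling, exposure and TRDF/ERDF times are capped by visit or discontinuation dates, and step 5.2.1 cannot affect Week 48 for these participants. Early by-visit Snapshot categories, the Table 8 Follow-up slot and on-treatment adverse events may differ. Most adverse event displays are by Maintenance Phase, which does not use the 63-day rule.

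**What to change.** In Table 16, define the Q8W on-treatment limit as last injection + 35 days when a lead-in participant's last injection is Week 4B, and keep + 63 from the Week 8 injection onwards. Carry the same condition into the Maintenance-phase derivations that reuse 63: the Table 8 Follow-up slot, Appendix 9 step 5.2.1, Appendix 10 and exposure in section 15.6.4. Table 9 needs no change, because these participants do not reach the Extension Phase.

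Also reconcile the under-dosing rule in section 15.1.1, which counts days beyond 56 for the Week 8 injection of Q8W lead-in participants, with the 28-day interval used elsewhere in the SAP. This concerns analysis definitions only, not dosing.

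The cost is one conditional line in the SAP and in the derivation code. If the sponsor prefers to leave Table 16 as it is, a pre-specified sensitivity analysis with one common window after Week 4B would show whether the choice matters.
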